This protocol describes a study intended to evaluate the Cionic Neural Sleeve for subjects diagnosed with KOA. CIONIC will use this study as an opportunity to validate FES for disuse atrophy in KOA. CIONIC will use lab visits (Table 1) to record participants' strength, kinematic gait metrics, walking performance, self-reported functional capacity and pain.

The Cionic Neural Sleeve has been evaluated for safe use in a simulated at-home environment under prior studies (CIONIC-02-001 and CIONIC-03-001).

There are two specific aims with this study:

Aim 1 – Validate FES for disuse atrophy in KOA

The study intends to obtain evidence to support the use of the FES for disuse atrophy in the KOA community. Standard clinical assessments will be collected at meaningful endpoints in the study to allow CIONIC to measure subjects' performance over time.

Aim 2 - Provide statistically significant evidence

The study design is a randomized controlled trial, where CIONIC will collect spatial and kinematic metrics to track participants' mobility and gait patterns. Some examples of these metrics may include: gait speed, total steps, step variability, and foot-floor angle at heel strike.

Table 1: Schedule of events

Initial visit	
 • Verify consent • Gather demographic information and anthropometric measurements • Measure strength, walking performance, thigh muscle volume, functional ability of the lower limb • Distribute questionnaires on perceived functional capacity, pain, and quality of life • Prescribe exercise and walking program • Random assignment of groups • Distribute the Cionic Neural Sleeve and provide Instructions for Use
6 week study midpoint	
 • Measure strength, walking performance, thigh muscle volume, functional ability of the lower limb • Distribute questionnaires on perceived functional capacity, pain, and quality of life
End of study	
 • Measure strength, walking performance, thigh muscle volume, functional ability of the lower limb • Distribute questionnaires on perceived functional capacity, pain, and quality of life • Collect equipment

Participation Selection and Randomization

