The study will be explained to the participants and written informed consent will be obtained before the initial lab visit. Physical measurements, performance tests, and questionnaire responses will be collected at three lab visits: initial, study midpoint (6 weeks), and end of study (12 weeks). Physical measurements will include height, weight, and thigh circumference of the impacted leg. If subjects report bilateral compromised legs, the most impacted/painful leg will be measured. Participants will be asked to complete four performance tests (maximal voluntary isometric contraction of the quadriceps, Five Times Sit to Stand Test (FTSST), 10-meter Walk Test (10mWT), and the 6-Minute Walk Test (6MWT)) and three questionnaires (Western Ontario/McMaster Universities Osteoarthritis Index physical function (WOMAC-PF) subscale, WOMAC-pain, and the Short Form-36). Order of the tasks at the lab visits are as follows: maximal voluntary isometric contraction of the quadriceps, FTSST, 10mWT, WOMAC-PF, 10mWT, WOMAC-pain, 6MWT, Short Form-36, and 6MWT. Instruction will be provided to the participants before beginning a new task, and the researchers will periodically gauge the subjects for a need for a break and understanding of the task. For the walking tests, subjects will be fitted with the electrical stimulation system to collect EMG/kinematic data, and depending on the subject's group assignment, stimulation may or may not be enabled. All subjects will be provided with and instructed to wear the electrical stimulation system for the subsequent 12 weeks. All subjects will be taught how to navigate the supporting app and receive a user manual on how to operate/care for the system. Subjects assigned to receive stimulation will be taught how to adjust parameters of the device using the supporting app. All participants will receive a handout explaining the exercise, and a calendar for the exercise and walking program (Appendix

B). Subjects will be informed to perform the exercise and walking program in an area free from obstacles. Lab visits may be up to 90 minutes in duration.

Exercise and Walking Program

The participants will wear the device during the 12-week exercise and walking program. This may range from 1 minute to 35 minutes per day (Appendix B).

Exercise Program

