The WOMAC-PF is a 17-item questionnaire that measures the impact of KOA on daily physical activities in the past 48 hours²⁶. Scores on the WOMAC-PF range from 0 to 68, with high scores indicative of worse functional limitations²⁶. The minimal clinically important difference (MCID) for improvement of 14.48²⁷ will be used as a benchmark.

Pain

The WOMAC-Pain is a 5-item survey that prompts the respondent to reflect on the quality of pain in 5 activities during the last 48 hours²⁶. Scores range from 0 to 20, with high scores indicative of worse pain²⁶, and the MCID of 8.74²⁷ will be used as an indicator of improvement in our study.

Walking Performance

Walking performance will be evaluated by gait speed and walking endurance. All subjects will wear the Cionic Neural Sleeve during the walking tests, and all subjects will perform the same number of tests. The control group will perform the walking tests in unstimulated conditions. Unstimulated conditions require subjects to wear the Cionic Neural Sleeve as they traverse to collect EMG/kinematic data, but stimulation will not be enabled. Subjects assigned to receive the stimulation intervention will perform the walking tests in unstimulated conditions before traversing in stimulated conditions. Stimulated conditions require subjects to wear the Cionic Neural Sleeve and receive stimulation assistance while walking.

Gait speed (m/s) will be measured using the 10mWT on a 10-meter walkway with brightly colored tape to indicate boundaries, two chairs, a stopwatch/timer, and the subject's usual walking aid. During this performance test, the subject will walk with the Cionic Neural Sleeve for 10 meters, and time will be measured for the intermediate 6 meters. Two trials will be administered at the subject's comfortable walking speed, followed by two trials at fast walking speed. Rests will be provided between each trial. The trials for each speed and stimulation condition will be averaged. Acceleration and deceleration will occur outside of the timed portion to allow for a more accurate assessment²⁸. Prior literature reported an improvement of 0.12 m/s in patients with unilateral KOA post-surgery^{29,30}, and this will be used as a point of comparison in our study.

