Appendix G: 10-Meter Walk Test

Meter 0 Meter 2
Start
Walk Start
Timing

Meter 8 Meter 10
End
Timing End
Walk

1. Subjects will walk with/without assistance for 10 meters.
2. Time will be measured for the intermediate 6 meters to allow for acceleration and deceleration.
3. Timing will start when the toes of the leading foot crosses the 2-meter mark.
4. Timing will stop when the toes of the leading foot crosses the 8-meter mark.
5. Assistive devices can be used but should be kept consistent and documented from test to test.
6. Collect two trials at the subject's comfortable walking speed, followed by two trials at their fast-walking speed.
7. Trials for each speed will be averaged.

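### As written, the 10mWT averaging rule makes unstimulated gait speed a four-trial, two-test mean in controls but a two-trial, first-test mean in anyone whose second test is stimulated

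*Combined protocol and SAP*

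**What the plan says.** All references are to the combined protocol and SAP.

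- **Two tests per visit.** Lab Visits gives the task order after the strength test as "FTSST, 10mWT, WOMAC-PF, 10mWT, WOMAC-pain, 6MWT, Short Form-36, and 6MWT", so the 10mWT appears twice.
- **Same number in every arm.** Walking Performance says "all subjects will perform the same number of tests".
- **Condition by arm.** For controls: "The control group will perform the walking tests in unstimulated conditions". For the others: "Subjects assigned to receive the stimulation intervention will perform the walking tests in unstimulated conditions before traversing in stimulated conditions".
- **Trials within a test.** "Two trials will be administered at the subject's comfortable walking speed, followed by two trials at fast walking speed".
- **Averaging rule.** "The trials for each speed and stimulation condition will be averaged". Which of the two tests a trial came from plays no part in the rule.
- **Appendix G, step 7.** "Trials for each speed will be averaged".
- **Analysis.** Data Analysis/Statistical Analysis plans an ANOVA or Kruskal-Wallis test across conditions on the outcome variable. It does not say whether that is a follow-up value or a change, or which gait-speed value enters.

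No section says that the controls' second test is kept apart, discarded or paired with the stimulated test.

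**The concern.** Gait speed is part of a primary outcome, so the unstimulated value should mean the same thing in every arm. Under the averaging rule it need not. A control's second test has the same speed and condition as the first, so the two fall into one average. A participant who is stimulated in the second test has only the first test in the unstimulated average.

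The second test comes after the first and after a questionnaire. If people speed up with practice or slow down with fatigue, the control average contains half of that shift and the other average contains none of it. Practice would raise the control value and understate a benefit of stimulation; fatigue would do the opposite. Averaging the controls' two tests also hides their second-minus-first difference. That difference is the only direct estimate of the order effect in a design where the stimulated walk always comes second.

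**Working it through.** The plan gives no power figure or variance for gait speed (Appendix A covers WOMAC measures only), so there is no stated result to reproduce. The check is a count followed by simple algebra.

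**1. Trial count per speed at one visit**

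Inputs: 2 tests (Lab Visits) and 2 trials per speed per test (Walking Performance).

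| Participant | Unstimulated trials | Stimulated trials |
|---|---|---|
| Control | 2 × 2 = 4 (tests 1 and 2) | 0 |
| Second test stimulated | 1 × 2 = 2 (test 1) | 1 × 2 = 2 (test 2) |

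NMES+FES belongs in the second row. NMES+ is uncertain: it is assigned to stimulation, but the Overview of Study gives it unstimulated walking in the home programme, and its second-test condition is not stated. If it is tested unstimulated, it has four trials like controls.

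**2. Offset at a single visit**

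Let m be mean speed in test 1 and m + b the mean in an unstimulated test 2.

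- Control average: (2m + 2(m + b))/4 = m + b/2
- Second test stimulated: m
- Difference with no treatment effect: b/2

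The documents do not give b. For assumed values, against the 0.12 m/s comparison value in Walking Performance:

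| b (m/s) | b/2 (m/s) | b/2 ÷ 0.12 |
|---|---|---|
| 0.02 | 0.01 | 8.3% |
| 0.04 | 0.02 | 16.7% |
| 0.06 | 0.03 | 25.0% |

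A negative b gives the same sizes with the sign reversed.

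**3. Does it cancel in change from baseline?**

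Let b₀ and b₁₂ be the shifts at baseline and week 12.

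- *Allocation known before the baseline walks.* Controls carry b₀/2 then b₁₂/2; stimulated walkers carry 0 at both visits. The spurious difference in change is (b₁₂ − b₀)/2. It is zero if b is stable. If b falls from 0.04 to 0, it is −0.02 m/s, or 16.7% of 0.12 in size.
- *Allocation made after the baseline walks.* Assume everyone then walks both baseline tests unstimulated, so all baselines carry b₀/2. The change is shifted by (b₁₂ − b₀)/2 in controls and by −b₀/2 in stimulated walkers. The difference is b₁₂/2, so nothing cancels.

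The documents point both ways on the order. Table 1 lists "Random assignment of groups" after the walking measurements. Lab Visits makes stimulation in the walking tests depend on group assignment and describes this for all three visits, the first included.

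**4. Precision**

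With total variance set to 1 and an assumed trial intraclass correlation (ICC), the variance of a mean of k trials is ICC + (1 − ICC)/k.

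- ICC 0.70: 0.775 for four trials, 0.850 for two; ratio 0.91
- ICC 0.95: 0.9625 for four trials, 0.975 for two; ratio 0.99

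Using two trials in controls instead of four therefore raises the variance of their value by about 1% (0.975/0.9625) to 10% (0.850/0.775).

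**The case against.** The strongest reply is that pooling is inferred. The averaging sentence closes the description of one administration of the test, so the trials it means may be just the two per speed in that test. On that reading every arm has two trials per test and there is no mismatch. Giving controls the same number of tests may also have been meant to supply a position-matched second walk, which pooling would defeat. This reading is possible, but it is not written. Stimulation condition does not vary within one test, so a rule that sorts trials by condition most naturally spans the visit.

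The reply on size is fair. Both the value and the sign of b are unknown, and the rests between trials and the questionnaire between tests should limit fatigue, though not practice. With 45/3 = 15 per arm (assuming equal allocation and no dropout) and an assumed between-person SD of 0.15 to 0.25 m/s, the standard error of an arm difference is SD × √(2/15), about 0.055 to 0.09 m/s. An offset of 0.01 to 0.03 m/s is well inside that.

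Three stronger readings are tempting, and the documents do not support them.

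- *Appendix G contradicts the main text and mixes stimulated with unstimulated trials.* The appendix describes a single test and never mentions a second one or stimulation condition. Step 7 is incomplete, but it does not clearly conflict.
- *Table 1 proves that allocation follows the baseline walks.* It is a bullet list of visit contents with no stated sequence, and Lab Visits suggests the opposite.
- *Both stimulation arms are affected.* That depends on how NMES+ is tested, which is not stated.

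**Conclusion.** The point holds as a defect in a stated rule. As worded, the rule makes unstimulated gait speed a four-trial, two-test mean in controls and a two-trial, first-test mean in participants whose second test is stimulated: NMES+FES, and NMES+ only if it too is tested stimulated. The resulting offset is b/2, or 0.01 to 0.03 m/s (8% to 25% of 0.12 m/s) for an assumed b of 0.02 to 0.06 m/s of either sign. It remains in an ANOVA on follow-up values. In change scores it disappears only if allocation precedes the baseline walks and b is stable, and the documents do not settle the order of allocation.

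A reader might infer an established bias of known direction in a primary outcome. That goes too far: the documents give no value of b, a per-test reading of the rule cannot be excluded, and the offset may cancel. This is a cheap improvement worth making before analysis, not proof that the gait-speed comparison is invalid.

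**What to change.** In Walking Performance, replace the averaging sentence with a rule to this effect:

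- Trials are averaged by speed within each 10mWT and never across the two tests.
- Unstimulated gait speed for arm comparisons is the mean of the two first-test trials per speed, in every arm and at every visit.
- Any comparison of the stimulated (second) test with controls uses the controls' second test.

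The third line matters. Restricting every arm comparison to the first test would leave the stimulated walk without a control walk in the same position. In Appendix G, add *within each test* to step 7.

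The trial count is then two in every arm, and the b/2 offset in the unstimulated value is zero whatever b is, whenever allocation occurs and however NMES+ is tested. The cost is two small text changes, no new data, and the 1% to 10% rise in the variance of the control value shown above.

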This study is a randomized controlled trial. Figure 2 depicts a flow diagram of the study design. Participants will be screened for eligibility through a questionnaire, and after study details are explained and consent is obtained, they will be invited to the study site. Assessments will be conducted at CIONIC Inc., and involve approximately 45 patients for a 12 week study period.

CIONIC

CIONC FOR ORTHOPEDICS

All subjects will be assigned an electrical stimulation system to wear on the most impacted leg and be prescribed a home-based exercise and walking program. Subjects will be randomly assigned into three groups: (a) control; (b) NMES+; (c) NMES+FES. The control group will not receive stimulation for the exercise and walking program, whereas subjects in NMES+ will receive stimulation during exercises, and subjects in the NMES+FES group will receive stimulation during exercises and walking. Outcome measures will be assessed at baseline, 6 weeks after baseline, and end of study (Table 2). Equipment and additional feedback will be collected at the end of study. These three groups will be analyzed using several outcome measures. Primary outcome measures of the study are quadriceps strength, perceived functional capacity, self-reported pain, and walking performance. Secondary interest will be adherence to program, thigh muscle volume, functional ability of the lower limb, and quality of life. The CIONIC system will be used to track adherence (duration of sessions, frequency of use).

[figure not shown]

Figure 2: Study flow

Table 2: Study overview

Comparison Groups	Treatment Schedule	Timing and Outcome Measures
Control (unstimulated exercise and walking)	Exercise: 5x/week for 12 weeks Progression every 3 weeks	At baseline, midpoint and end of study: Quadriceps strength Perceived functional capacity Self-reported pain Walking performance Thigh muscle volume Functional ability of lower limb Quality of life EMG activity
NMES+ (NMES+exercise and unstimulated walking)	Walking: 10 min, 3x/week for 12 weeks Progression up to 30 min by end of study	Weekly: Adherence to program
NMES+FES (NMES+exercise and FES+walking)		

Participant Identification, Recruitment & Informed Consent

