Walking endurance (m) will be measured using the 6MWT using the same walkway utilized for the 10mWT. Participants will wear the Cionic Neural Sleeve during the two 6MWTs. For the 6MWT, the subject will be instructed to walk as far as possible for 6 minutes, up and down the pathway, and pivoting to turn at the end of each lap³¹. Timing will begin when the participant steps over the start line, and distance traveled will be recorded. Encouragement outlined in the guideline (Appendix C) will be given to the subjects after each minute, and participants will be instructed to stop at 6 minutes or prior, if they are unable to complete 6 minutes. Use of a walking aid and standing rests will be permitted. Normative values of people aged 40-80 years will be used as reference values³².

Secondary Measures

Adherence to Program

Adherence to the program will be measured by the usage log of the Cionic Neural Sleeve. The data collected from the Cionic Neural Sleeve worn on the affected limb/most affected limb will be recorded to monitor compliance to the program in number of repetitions and duration of walking.

Thigh Muscle Volume

Thigh muscle volume will be estimated using a measurement tape for thigh circumference and a prediction model. Thigh circumference (cm) will be measured from a point 15 cm proximal to the superior pole of the patella. The prediction model is as follows: Muscle volume (cm³)

=4226.3 – 42.5×age(year) – 955.7× gender(male=1, female=2) + 45.9×body weight(kg) + 60.0×thigh circumference(cm)³³. It was selected for this study for its correlation ($r^2 = 0.745$) to magnetic resonance imaging, the gold standard of measuring muscle volume³⁷.

Functional Ability of the Lower Limb

To measure functional ability of the lower limb, subjects will be asked to perform the FTSST. The FTSST requires participants to sit in a chair with their arms crossed over the chest and then to stand up/sit down for five times, as fast as possible³⁴. Subjects will be timed from the initial sitting position to the final standing position. Cut-off points of 10.8 and 12.8 seconds will be used as references for intermediate and poor function, respectively³⁵.

Quality of Life

The Short Form 36 (SF-36) is a generic measure of health status that measures self-reported functional health and well-being in the past four weeks in eight domains or two summary scores. Scores range from 0 to 100, with 0 representing extreme interference, and 100 representing no interference³⁶.

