Other information to be collected include date of birth, gender, ethnicity, height, weight, duration of condition, and type and dosage of medication.

Data Analysis/Statistical Analysis

For each of the primary and secondary measures, we will perform a Shapiro-Wilk test for normality to assess the assumption of normality. If the outcome variable is approximately normally distributed, a paired t-test will be used to statistically compare outcome metrics before and after the intervention within a condition. If the normality assumption is not met, the Wilcoxon signed rank test will be used as an alternative to the paired t-test for this statistical comparison. Bonferroni multiple hypothesis correction will be utilized for a corrected significance level.

To compare across conditions, an analysis of variance (ANOVA) test will be performed if the outcome variable is normally distributed. If the normality assumption is not met, the Kruskal Wallis test will be used as the non-parametric version of ANOVA. We may also employ a repeated measures ANOVA test for inclusion of all three timepoints.

Organizational Relationships

CIONIC works closely with Edge Analytics, a consulting firm who has been contracting for CIONIC for over two years. The firm is primarily responsible for algorithm development and statistical analyses of kinematic and EMG data. [name], [name], and [name] are employees of Edge Analytics who have been working closely with Cionic. [name] is a sub-investigator on this study.

Risk & Benefit Assessment

The Cionic Neural Sleeve has been tested extensively in previous studies. Across these prior studies, the Cionic Neural Sleeve has been evaluated for walking and exercise mode, approved for FDA 510k submission and its intended use in a simulated home environment, and for home usability with no adverse events.

However, any study of this kind comes with some known risks, that although rare, are associated with participation:

- Discomfort from the electrical stimulation
- Minor skin irritation at the sites of sensor/electrode pad placement
- Muscle fatigue from prolonged device use
- Anxiousness due to the anticipation of receiving an electrical stimulation
- Injury caused by unintended falls while using the Cionic Neural Sleeve
- Exposure to coronavirus disease 2019 (COVID-19) or other communicable disease

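### Minor: the change in predicted thigh muscle volume counts 1 kg of body weight as 0.765 cm of treated thigh, and the plan does not show that it tracks change in that thigh

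*Combined protocol and SAP*

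**What the plan says.** The Thigh Muscle Volume section, under Secondary Measures, states: "Thigh muscle volume will be estimated using a measurement tape for thigh circumference and a prediction model". The printed model has an intercept of 4226.3, a term of −42.5 per year of age and a term of −955.7 × gender. The other two terms read "45.9×body weight(kg) + 60.0×thigh circumference(cm" (the quote stops before the closing bracket). The reason for choosing the model begins "It was selected for this study for its correlation"; the figure given is r² = 0.745 with magnetic resonance imaging.

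On timing, Lab Visits says "Physical measurements, performance tests, and questionnaire responses will be collected at three lab visits", namely baseline, 6 weeks and 12 weeks, and adds "Physical measurements will include height, weight, and thigh circumference of the impacted leg". The measured leg is the impacted or more painful one, which is also the leg that wears the device (Overview of Study).

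On status, Overview of Study says "Secondary interest will be adherence to program, thigh muscle volume, functional ability of the lower limb, and quality of life". On analysis, the Data Analysis/Statistical Analysis section covers every primary and secondary measure. If the data look normal, "a paired t-test will be used to statistically compare outcome metrics before and after the intervention within a condition", with the Wilcoxon signed rank test otherwise. Arms are compared by ANOVA or Kruskal-Wallis. The plan mentions neither an analysis of the raw circumference nor any handling of weight change.

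**The concern.** The intervention acts on one thigh. The model contains one measurement of that thigh; its other inputs are age, gender and whole-body weight. A model chosen because it predicts volume is then used to measure change within a person over 12 weeks. Nothing in the plan speaks to that second use.

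The Hypotheses section names muscle mass, and Aim 1 is about disuse atrophy. Predicted thigh volume is the only outcome that addresses muscle size. If a group's mean weight drifts during the study, its paired test can show a rise or fall in muscle volume although the thigh has not changed, or can hide a change that did occur. Randomisation does not protect a within-group test from this.

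**Working it through.** The plan gives no derived figure or sample size for this outcome, so there is none to reproduce. The check is to difference the printed formula.

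**Inputs (Thigh Muscle Volume section):** weight 45.9 cm³ per kg; circumference 60.0 cm³ per cm; age −42.5 cm³ per year. Intercept and gender are constant within a person and cancel.

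**Change score with same-visit inputs:**
change in volume = 60.0 × ΔC (cm) + 45.9 × ΔW (kg) − 42.5 × Δage (years)

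**Exact consequences**
- Weight against circumference: 45.9 / 60.0 = 0.765 cm of thigh per kg.
- Age, if entered exactly: 42.5 × 84 / 365.25 = 9.8 cm³ lost over 12 weeks in every participant, or 9.8 / 60.0 = 0.16 cm. If age is entered in whole years, a participant with a birthday in the interval loses 42.5 cm³ and the others lose nothing.
- Illustration: a 1 cm thigh gain with a 1 kg loss scores 60.0 − 45.9 = +14.1 cm³. With a 2 kg loss it scores 60.0 − 91.8 = −31.8 cm³. Both leave out the age term. No passage predicts such a pattern.

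**Within-group mean shift with no thigh change** (the weight shifts are assumptions)

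| Mean weight shift | Shift in mean volume | Equivalent circumference |
|---|---|---|
| 0.5 kg | 22.95 cm³ | 0.38 cm |
| 1 kg | 45.9 cm³ | 0.765 cm |
| 2 kg | 91.8 cm³ | 1.53 cm |

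**Between arms.** Compared with circumference alone, and with uncorrelated changes, the variance of the change score is inflated by 1 + (45.9 × SDw)² / (60.0 × SDc)². The documents give neither SD of change, so these are assumed ranges:

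| | SDw 0.5 kg | SDw 1 kg | SDw 2 kg |
|---|---|---|---|
| SDc 1 cm | 1.15 | 1.59 | 3.34 |
| SDc 2 cm | 1.04 | 1.15 | 1.59 |

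**Correlated changes.** With an assumed correlation of 0.5 and SDs of 1 cm and 1 kg, the variance ratio is (3600 + 2106.81 + 2754) / 3600 = 2.35. The squared correlation of volume change with circumference change is (60 + 22.95)² / 8460.81 = 0.81, against 3600 / 5706.81 = 0.63 when uncorrelated. A larger variance ratio therefore need not mean worse tracking of the thigh, and the ratio is only a rough guide.

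**Weight and age held at baseline.** The change reduces to 60.0 × ΔC, which is circumference change on another scale.

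**The case against.** The target is muscle volume, not circumference. In a joint model the weight coefficient applies with circumference held fixed and may carry real information about muscle. This stands. A reader might infer that the change score is a poor measure, but the documents do not say how much of the weight term is muscle. They support only the statement that the score is not shown to track change.

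The main hypothesis is comparative, and the arms follow the same exercise and walking programme. This also stands. A reader might infer bias in the comparison of arms. That would need mean weight change to differ between arms, and nothing in the documents suggests it does. The age term with exact age is the same in every arm.

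A reader might also infer a scheduling conflict, because Table 1 puts "Gather demographic information and anthropometric measurements" at the initial visit only. The documents do not bear this out. Table 1 also lists thigh muscle volume at all three visits, its inputs can be read as part of that entry, and Lab Visits places weight and circumference at all three.

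Finally, weight might be carried forward from baseline, which would remove the effect. The plan does not say so, and Lab Visits points the other way.

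None of this supplies evidence that the model follows change over 12 weeks, or protects the paired tests from a mean weight shift.

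**Conclusion.** The point holds as a minor one about a secondary outcome on which no sample-size calculation depends. The coefficient arithmetic is exact: 1 kg counts as 45.9 cm³, or 0.765 cm of treated thigh. It rests on same-visit values entering the formula, which is the ordinary reading. The 9.8 cm³ fall over 12 weeks further assumes that age is entered exactly.

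The practical exposure is in the within-group paired tests, where any mean weight shift moves the result without a change in the thigh. In the comparison of arms the effect is mainly loss of precision. On the assumed SDs with uncorrelated changes, it runs from negligible (1.04, at 2 cm and 0.5 kg) to large (3.34, at 1 cm and 2 kg). If weight is stable, little is lost.

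**What to change.** Two additions to the Data Analysis/Statistical Analysis section:

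1. Alongside predicted volume, analyse change in the directly measured treated-leg thigh circumference (15 cm above the patella), adjusted for its baseline. This compares arms on the same information as computing volume change with weight and age held at baseline.
2. State that a change in predicted volume will not be read as measured change in muscle mass unless the change in circumference agrees.

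Predicted volume stays in the plan, and no single rule for the weight input need be imposed.

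The cost is one or two sentences and no new data, since circumference is already collected. The downsides are one more reported analysis, and that tape circumference includes fat and is not itself validated against muscle in the documents. Weight change can still reach it through the thigh, so it is a check on predicted volume and not a substitute for imaging.
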